## **15. Potential Benefits to Participants**

Voxelotor is being offered as a treatment for your SCD for the reasons previously indicated. If it is effective, symptoms of SCD may improve, however participants may or may not receive any benefit from being in this Study. It is possible that your symptoms may get better, stay the same or get worse. This study is designed to learn more about the effects of a novel treatment for sickle cell disease (voxelotor) on the brain. We hope that the study results will be used to help others in the future.

## **16. Compensation to Participants**

Subjects will be compensated for their time. A \$50.00 gift card will be given to the subject after completion of each measurement session, for a total up to \$250.00 for the completion of all study measures.

## **17. Statistical Considerations, Data Management and Confidentiality**

### **17.1 Statistical Considerations**

#### **Statistical Hypothesis**

- Primary Endpoint: CBF and OEF are significantly lower at 4 and 12 weeks of treatment with voxelotor compared to pre-treatment levels. Paired t-test or Wilcoxon signed-rank test will be used to evaluate results, as patients are their own controls.
- Secondary Endpoints: The change in OEF and CBF from pre-treatment levels are significantly correlated with the change in hemoglobin. The change in OEF and CBF from pre-treatment levels are correlated with markers of hemolysis.

#### **Sample Size Determination**

This is a pilot study involving 50 participants to define the magnitude of change. Power cannot be calculated at this time.

#### **Populations for Analyses**

There will be one dataset for this pilot study of 50 participants.

### **17.2 Statistical Analyses**

#### **General Approach**

As the primary objective of this study is to obtain clinical and laboratory information to justify a larger clinical efficacy trial of voxelotor in SCA patients, the results of this study will be descriptive.

#### **Analysis of the Primary Efficacy Endpoint**

To test our hypothesis that voxelotor reduces oxygen extraction and blood flow, we will compare changes in the DCS/FDNIRS-measured outcome variables (CBF, OEF, CMRO2) from baseline levels using one-sample paired t-test or Wilcoxon signed-rank test, as appropriate. Measures will be adjusted for the increase in hemoglobin observed (i.e., relative change in OEF per g/dL change in hemoglobin).

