## 2. Objectives and Endpoints

OBJECTIVES	ENDPOINTS	JUSTIFICATION FOR ENDPOINTS
Primary		
Evaluate the cerebral hemodynamic effects of voxelotor	Change in CBF, OEF and CMRO2 from baseline at Week 4 and 12	Voxelotor is a promising new drug that improves hemoglobin levels and reduces the incidence of worsening anemia in SCD. However, it is unclear whether this increase in hemoglobin is associated with reductions in blood flow and oxygen extraction in the brain
Secondary		
Evaluate the relationship between CBF, OEF, CMRO2 and change in total Hb levels	Correlation of CBF, OEF, CMRO2 and change in total Hb levels from baseline	By increasing hemoglobin levels, voxelotor may show improvement in CBF, OEF, CMRO2 akin to the effects of blood transfusion but without the detrimental side effects.
Evaluate the relationship between CBF, OEF, CMRO2 and voxelotor-modified Hb levels	Correlation of CBF, OEF, CMRO2 and level of RBC content of voxelotor-modified Hb	Voxelotor modification of Hb correlate to improvement of anemia. Quantified level of Hb modification (via HPLC or PK) may correlate with improvement in CBF, OEF, CMRO2
Exploratory		
Evaluate the relationship between CBF, OEF, CMRO2 and measures of RBC health	Correlation of CBF, OEF, CMRO2 and change in markers of RBC hemolysis (LDH, indirect Bil) and morphology (blood smear, RBC indices, retic, dense cells, and adhesion) from baseline	Restored RBC health is measured by reduction in hemolysis (measured by blood chemistry labs) and improvement in RBC morphology. Measured improvements in RBC health may correlate with

[figure not shown]
OBJECTIVES	ENDPOINTS	JUSTIFICATION FOR ENDPOINTS
		improvement in CBF, OEF, CMRO2

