## 5.3 Efficacy, Safety, and Other Assessments

Screening will occur up to 28 days prior to the start of the study. The subject's medical chart will be used for screening and for part of collection of trial data, per Health Insurance Portability and Accountability Act (HIPAA) rules, other relevant federal or state laws, and local institutional requirements, as applicable. Information obtained from the medical chart will include:

- a) List of current medications and their doses
- b) Vital signs

- c) Transfusion history
- d) Stroke history
- e) Previous MRI and/or MRA's
- f) Previous sleep studies
- g) Previous transcranial Doppler ultrasound results.

The study procedures and evaluations to be done as part of the study to support the determination of efficacy, as per the primary and secondary objectives outlined in this protocol, will include:

- **DCS/FDNIRS assessments.** Measurements of cerebral blood flow, oxygen extraction, and oxygen metabolism will be made by a trained study staff personnel using a customized diffuse correlation spectroscopy combined with frequency domain near infrared spectroscopy oximeter (Figure 2). A DCS/FDNIRS optical sensor will be manually held over the right and left forehead to obtain a brief (<1min) resting state measure of brain hemodynamics.

Measurements will be repeated up to 3 times per hemisphere (Figure 3). Total time of exam is typically 15-30 minutes. Measurements will be made before, and at 4 and 12 weeks after the start of voxelotor. Measurements will be obtained in quiet area of Aflac outpatient clinics using PPE and hand hygiene practices according to hospital policy.

- A research blood specimen will be obtained when a clinical sample is unavailable. Up to sixteen mLs of venous blood will be collected at each visit. Laboratory assessments relevant to measures predictive of voxelotor response and to measures of RBC Health will be performed at local (central CHOA lab) clinical labs. Local laboratory assessments will include complete blood count, reticulocyte count, hemoglobin electrophoresis, RBC dense cells and measures of RBC hemolysis (LDH, indirect bilirubin). RBC health laboratory assessments will include but are not limited to RBC adhesion.
- **Procedures that will be completed during the study as part of regular standard of clinical care:** These include physical examination, vital sign assessment (heart rate, blood pressure, pulse oximetry, etc.), medical history.

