## **13. Withdrawal of Participants**

### **13.1 Discontinuation of Study Intervention**

At any point in the study, the child or parents can withdraw from the study. Discontinuation from voxelotor treatment will end participation in the study.

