### **13.2 Participant Discontinuation/Withdrawal from the Study**

Participants are free to withdraw from participation in the study at any time upon request. An investigator may discontinue or withdraw a participant from the study for the following reasons:

- Pregnancy
- Significant study intervention non-compliance
- If any clinical adverse event (AE), such as hypersensitivity to the study drug, laboratory abnormality, or other medical condition or situation occurs such that continued participation in the study would not be in the best interest of the participant
- If the participant meets an exclusion criterion (either newly developed or not previously recognized) that precludes further study participation
- Disease progression which requires discontinuation of the study intervention

The reason for participant discontinuation or withdrawal from the study will be recorded on the Case Report Form (CRF). Subjects who sign the informed consent form and subsequently withdraw, or are withdrawn or discontinued from the study, will not be replaced.

Once dosed, participants who discontinue/withdraw the study will not be replaced. We estimate 40 subjects will be sufficient to achieve the primary, secondary, and exploratory endpoints. Our target sample size of 50 allows for approximately 20% drop out rate. This dropout rate far exceeds the actual dropout rate in the large multicenter Phase 2a study of voxelotor use in pediatrics (GBT440-007).

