#### **Analysis of the Secondary/Exploratory Endpoints**

Linear mixed-effects regression models with random-intercept at the patient level will be used to examine the association of each outcome measure (OEF, CBF, and CMRO2) with demographical (sex and age) and laboratory data (Hb, reticulocyte count, bilirubin, LDH, Hb occupancy, oxygen dissociation curves, RBC deformability and

mitochondrial content). These models will be two-level and will account for repeated measures (0, 4, and 12 week measurements) nested within the same patient.

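### The Week 12 primary test is a completer analysis with no plan for missing scans; a repeated-measures model on all scans would reduce, but not abolish, the possible bias

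*Combined protocol and SAP*

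**What the plan says.** - **Endpoint.** Section 2 gives the primary endpoint as "Change in CBF, OEF and CMRO2 from baseline at Week 4 and 12". The study schema in section 5.1 lists 12 weeks only.
- **Scans.** Section 5.3: "Measurements will be made before, and at 4 and 12 weeks after the start of voxelotor". The schedule in section 5.2 shows no scan at the end-of-study visit.
- **Primary test.** Section 17.2 compares the three outcomes "from baseline levels using one-sample paired t-test or Wilcoxon signed-rank test, as appropriate", and then adjusts for the rise in hemoglobin per g/dL.
- **Leaving the study.** Section 13.1: "Discontinuation from voxelotor treatment will end participation in the study". Section 13.2 also lets the investigator withdraw a participant for, among other reasons, adverse events, laboratory abnormality or "Significant study intervention non-compliance". Participants are not replaced.
- **Allowance.** Section 13.2 regards 40 participants as sufficient and says: "Our target sample size of 50 allows for approximately 20% drop out rate". It adds that this is well above the rate in an earlier paediatric study, without giving that rate.
- **Analysis set.** Section 17.1: "There will be one dataset for this pilot study of 50 participants". Section 17 has no rule for missing scans and does not say who enters the Week 12 test.
- **A mixed model is already planned**, but only for secondary and exploratory associations: "These models will be two-level and will account for repeated measures (0, 4, and 12 week measurements) nested within the same patient". It has a random intercept per patient.

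**The concern.** A paired t-test or signed-rank test discards anyone without both scans. A participant who stops voxelotor leaves the study, and no later scan is scheduled. The Week 12 change is therefore estimated in those who stayed, and the Week 4 scan of someone who leaves afterwards has no influence on it. The mean change in stayers equals the mean change for everyone only if leaving is unrelated to outcome.

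Section 17.1 says the pilot is to measure the size of the change, and section 17.2 that it is to justify a larger trial. The estimate is thus the main product, and there is no control arm to expose selective loss. A later sample size varies with 1/(effect squared). With the SD held fixed, an effect overstated by 12% gives a trial with 1/1.12² = 0.80 of the participants it needs; at 2% the fraction is 1/1.02² = 0.96.

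**Working it through.** **The plan's own figure.** 40/(1 − 0.20) = 50, so enrolment and allowance agree. No power can be reproduced, because no effect size, SD or alpha is given.

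**Step 1: bias of the completer mean.** The documents give no SDs, correlations or loss mechanism, so these are assumptions: visit SD 1; true change −0.3 at Week 4 (D4) and −0.4 at Week 12 (D12); equal correlation ρ between visits of 0.5 to 0.7; all loss after Week 4; log-odds of loss rising by 0.5, 1.5 or 3 per SD unit as D4 shows less fall (odds ratios 1.6, 4.5 and 20).

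- Completer mean of D12 = −0.4 + β × (mean D4 in stayers + 0.3).
- β = cov(D4, D12)/var(D4) = (1 − ρ)/(2(1 − ρ)) = 0.5.
- Example: ρ = 0.5, 20% loss, log-odds 0.5. Mean D4 in stayers is −0.396, so the completer mean is −0.4 + 0.5 × (−0.096) = −0.448, and 0.048/0.40 = 12% too large.

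Overstatement of the Week 12 change (lower value ρ = 0.7, upper ρ = 0.5):

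| Loss | Log-odds 0.5 | Log-odds 1.5 | Log-odds 3 |
|---|---|---|---|
| 5% | 1.9–3.1% | 5.2–8.1% | 8.1–11.4% |
| 10% | 3.7–6.1% | 9.9–15.2% | 14.8–20.8% |
| 20% | 7.3–12.0% | 18.7–28.3% | 26.9–37.6% |

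Rounded outward, this is about 2% to 12% at 5% loss and 7% to 38% at 20% loss.

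**Step 2: the model under the same assumptions.** In 6,000 simulated trials of 50 per case, at 5% and 20% loss, the likelihood estimate with unstructured covariance averaged −0.396 to −0.402 against the true −0.40. Its SD was within about 6% of the paired test's. With random loss of 20%, both were unbiased (SD 0.154 model and 0.159 paired at ρ = 0.5).

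**Step 3: where the model falls short.** A separate set of runs assumed true changes of −0.4 and −0.5, 20% loss, ρ = 0.6 and the poorest responders more likely to leave. Only the pattern should be relied on.

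| What drives loss | Paired test too large by | Model too large by |
|---|---|---|
| Week 4 change, loss after the scan | 24% | 0% |
| Week 4 change, half of losses before the scan | about 24% | 8% |
| Week 4 change, all losses before the scan | 24% | 15% |
| Unseen Week 12 change | 49% | 37–41% |

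Over the other correlation patterns tried, the model's bias ran from 8% to 26% with loss before Week 4 and from 32% to 47% with loss driven by Week 12. It was smaller than the paired test's in every informative-loss case.

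**Step 4: covariance structure.** When the three visit correlations were unequal (0.7/0.5/0.7 or 0.8/0.4/0.6), a random-intercept model was still 13% to 14% too large in the observed-loss case. The unstructured model was within 3% of the truth.

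**Step 5: a different quantity.** If leavers have a share f of the stayers' change and a fraction d leave, the stayers' mean divided by the all-participant mean is 1/((1 − d) + d·f). With f = 0 this is 1.25, 1.11 and 1.05 at d = 20%, 10% and 5%; with f = 0.5 it is 1.11, 1.05 and 1.03. No repeated-measures model can recover this from the planned data, because no scans follow stopping.

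**The case against.** The strongest reply is that this is a pilot with results called descriptive and no stated power, so a paired test is a reasonable choice. Several parts of that case stand.

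- The 20% is an allowance. A reader might infer that only 40 of 50 are expected at Week 12; section 13.2 does not say so.
- The listed withdrawal reasons do not include scan values. A link between leaving and CBF or OEF, and hence the direction of any bias, is assumed. The larger percentages need strong selection.
- A reader might infer that a mixed model removes the problem at no cost. Step 3 shows otherwise, and the model adds covariance and normality assumptions where the plan keeps a signed-rank option.
- One dataset of 50 is not contradicted by missing scans. Week 4 scans of later leavers still count in the Week 4 test.
- Stayers need not have tolerated full dosing, since section 4.1 allows reductions and interruptions.
- Withdrawal reasons are recorded (section 13.2) and individual data are to be listed (section 17.2), so some of the needed reporting is recoverable.

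The descriptive label does not answer the main point. If the estimate is to inform a larger study, the plan should say whom it describes and what it assumes about those missing.

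**Conclusion.** The Week 12 primary result rests on participants still in the study with both scans, and is unbiased only if loss is unrelated to outcome. The plan neither states nor examines that condition. Overstatement is possible, not established: about 2% to 12% at 5% loss and 7% to 38% at 20% loss, if loss depends on the Week 4 change as assumed. If loss is unrelated to outcome, there is no bias.

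The stronger reading, that the planned test will inflate the effect and that a mixed model cures it, is not supported. The model reduces bias to the extent that loss depends on scans already taken. It estimates the change had participants remained on voxelotor, not the effect regardless of stopping. It is still the better main estimate, because it uses every scan, had less bias in each informative-loss case tried, and has about the same precision.

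**What to change.** In section 17.2, primary analysis:

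1. Estimate the Week 4 and Week 12 changes, with 95% CI, from one linear mixed model per outcome. Use visit (0, 4, 12 weeks) as a categorical effect, unstructured within-patient covariance, and all dosed participants with a baseline scan. Use a random intercept alone only if the unstructured model does not converge.
2. Keep the paired t-test or signed-rank test as a completer sensitivity analysis, which also covers non-normal data.
3. State that the model targets the change had participants remained on voxelotor, and that it relies on loss depending on observed scans.
4. Add a sensitivity analysis giving leavers reduced or no change, for example f = 0.5 and f = 0 in Step 5.
5. Report the per-g/dL hemoglobin adjustment as a separate analysis.

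In section 17.1, define this analysis set. Report the number contributing at each visit, the timing and reasons for missing scans, and baseline and Week 4 values for those with and without a Week 12 scan.

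This needs new wording and no new data, and a related model is already planned. The price is the added covariance and normality assumptions.

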## 1. Study Summary

Study Title	ESR-C007: The Effect of Voxelotor on Cerebral Hemodynamic Response in Children with Sickle Cell Anemia
Phase	Single-center, open label pilot study.
Study Design	This study is a pilot, open-label, single-arm study to evaluate the effect of voxelotor on cerebral hemodynamics, as measured by diffuse correlation spectroscopy and frequency domain near-infrared spectroscopy (DCS/FDNIIRS) in patients 4 -30 years of age with sickle cell anemia (SCA). We hypothesize that as hemoglobin increases due to voxelotor, cerebral blood flow (CBF) and oxygen extraction fraction (OEF) will decrease. To test this hypothesis, CBF, OEF, and oxygen metabolism (CMRO 2 ) will be assessed by DCS/NIRS in participants prior to, periodically throughout, and after 12 weeks of treatment with voxelotor. The results of this study will be used to inform a larger study.
Primary Objective	The primary objective of this research is to evaluate the effect of voxelotor on CBF, OEF and CMRO 2 in children with SCA as assessed by change from baseline in DCS/NIRS at 4 and 12 weeks.
Secondary Objective	The secondary objective of this research is to evaluate the correlation between changes in CBF, OEF and CMRO 2 and change in markers of anemia, hemolysis and RBC health at 4 and 12 weeks.
Research Intervention(s)/Interactions	
The study intervention is voxelotor, administered orally. It will be used for the approved indication of sickle cell disease. This is a single-arm study. There is no control intervention.
 
Drug Intervention: Voxelotor
 

• Voxelotor tablets: 300 or 500 mg, administered orally

• Voxelotor dispersible tablets: 100 and/or 300 mg, administered orally

 
All participants will receive voxelotor. Participants 12 years or older will take 1500 mg/day. Participants younger than 12 years of age will receive a dose based on their body weight to provide exposure corresponding to the adult dose of 1500 mg/day.

Study Population	We plan to recruit male and female children ages 4-30 years with sickle cell anemia (HbSS, HbS/β  thal) who are followed in the Pediatric Sickle Cell Program at Children's Healthcare of Atlanta

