Voxelotor (Oxbryta) is a new drug for patients with sickle cell disease that improves hemoglobin levels and reduces the incidence of worsening anemia. However, it is unclear whether this increase in hemoglobin is associated with a reduction in cerebral metabolic stress. ***In this work, we will determine the effects of voxelotor on cerebral hemodynamics.*** We hypothesize that as hemoglobin increases due to voxelotor, cerebral blood flow and oxygen extraction fraction will decrease, similar to the effects of blood transfusion. To test this hypothesis, measurements of brain blood flow, oxygen extraction, and oxygen metabolism will be made using the [name] Lab’s customized diffuse correlation spectroscopy and frequency domain near-infrared spectroscopy system (DCS/FDNIRS). These well-validated, non-invasive optical techniques utilize near-infrared

**Figure 1, Hypothesized mechanism of ischemic injury in pediatric sickle cell disease** (Adapted from Juttukonda et al., JMRI 2019). As anemia worsens, arterial oxygen delivery is reduced. To compensate for this reduction, the cerebrovascular dilates to increase cerebral blood flow (red). As vascular reserve is exhausted and CBF plateaus, oxygen extraction fraction (blue) increases to preserve oxygen metabolism (green). Eventually there is a mismatch between tissue metabolic demand (dotted black) and oxygen metabolism, and infarction ensues. Transfusion acts to increase oxygen delivery and is thought to relieve metabolic stress by reducing oxygen extraction and cerebral blood flow and improving vascular reserve. We hypothesize that the increase in hemoglobin caused by voxelotor will act in a similar fashion to reduce oxygen extraction fraction and blood flow.

light to penetrate deep into tissue (~1-2 cm) in order to estimate an average oxygen saturation of the microvasculature, i.e., capillaries, arterioles, and venules. Our preliminary results with DCS/FDNIRS applied to children with sickle cell disease suggest that the techniques are sensitive to alterations in blood flow and oxygen extraction in these patients associated with changes in hemoglobin.

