## **9. Inclusion and Exclusion Criteria**

### **9.1 Inclusion Criteria**

Subjects will be recruited from the CHOA Aflac Sickle Cell Comprehensive Clinics located at the Scottish Rite campus and the Egleston campus.

In order to be eligible to participate in this study, an individual must meet all of the following criteria:

1. Written informed parental/guardian consent and participant assent for patients < 18y or written informed consent for patients > 18y has been obtained per institutional review board (IRB)/Ethics Committee (EC) policy and requirements, consistent with ICH guidelines.
2. Stated willingness to comply with all study procedures and availability for the duration of the study
3. Male or female participants, ages 4 to 30 years, inclusive
4. Homozygous hemoglobin SS (HbSS) or hemoglobin S/beta thalassemia (HbS/β thal
5. Hemoglobin (Hb): Hb ≤10.5 g/dL at baseline
6. Concomitant hydroxyurea (HU) therapy is allowed if the dose has been stable for at least 3 months with no anticipated need for dose adjustments during the study and no sign of hematological toxicity.
7. Ability to take oral medication and willingness to adhere to daily voxelotor and scheduled DCS/NIRS assessments.

8. If sexually active and female, must agree to abstain from sexual intercourse or to use a highly effective method of contraception throughout the study period and for 30 days after discontinuation of study drug. If sexually active and male, must agree to abstain from sexual intercourse or willing to use barrier methods of contraception throughout the study period and for 30 days after discontinuation of study drug.
9. Females of child-bearing potential, i.e., who have begun menstruation and are sexually active, are required to have a negative pregnancy test at screening before the initial administration of study drug.

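### A sentence in the primary analysis scales change by the hemoglobin rise, giving a quantity that is neither the primary endpoint nor the hypothesis, is spelled out only for OEF, and is not labelled supplementary

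*Combined protocol and SAP*

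**What the plan says.** The primary outcome appears several times, always without Hb scaling:

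- Section 1, Primary Objective: the effect on CBF, OEF and CMRO2 "as assessed by change from baseline in DCS/NIRS at 4 and 12 weeks".
- Section 2, primary endpoint: "Change in CBF, OEF and CMRO2 from baseline at Week 4 and 12".
- Section 5.1, Study Outcomes: change from baseline in the same three measures (there at 12 weeks only).
- Section 17.1, Statistical Hypothesis: "CBF and OEF are significantly lower at 4 and 12 weeks of treatment with voxelotor compared to pre-treatment levels".

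The Hb relationship is placed among the secondary endpoints in section 2: "Correlation of CBF, OEF, CMRO2 and change in total Hb levels from baseline". Section 17.1 repeats it as a secondary hypothesis, and section 17.2 gives the secondary endpoints a mixed model.

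The primary-analysis paragraph of section 17.2 opens in line with this: changes in the three measures are tested by paired t-test or Wilcoxon signed-rank test. It then adds: "Measures will be adjusted for the increase in hemoglobin observed (i.e., relative change in OEF per g/dL change in hemoglobin". No other section explains that sentence.

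**The concern.** The wording is mandatory and sits inside the primary analysis, but it introduces a different quantity in different units: percent per g/dL rather than change. Four things are not stated: whether the scaled value is additional to the plain change; how CBF and CMRO2 are to be scaled; whether the ratio is formed per patient or from group means; and what is done with a patient whose Hb does not rise.

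The last point can arise. The sentence presumes an increase, but eligibility only caps the starting value ("Hb ≤10.5 g/dL at baseline"), section 4.1 foresees missed doses, dose reductions and holds, and section 17.1 sets one dataset with no Hb-response condition.

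What is at stake is the figure passed on to the larger study. Section 17.1 gives the purpose: "This is a pilot study involving 50 participants to define the magnitude of change". If the sentence is left as it is, the choice of how to express that magnitude, and for which measures, can be made after the data are seen.

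**Working it through.** **Plan's own figure.** Section 13.2 gives 40 evaluable patients and about 20% dropout: 40 / (1 − 0.20) = 50, which matches the target. Section 17.1 states no power, and the documents give no effect size or SD. Below, n = 40 comes from section 13.2 and every other input is an assumption.

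**Arithmetic that needs no distributional assumption.** Per-patient ratio = relative OEF change (%) / Hb change (g/dL). For a 6% fall in OEF:

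| Hb change (g/dL) | Ratio (% per g/dL) |
|---|---|
| +1.0 | −6 / 1.0 = −6 |
| +0.1 | −6 / 0.1 = −60 |
| 0 | undefined |
| −0.2 | −6 / −0.2 = +30 |

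The same fall in OEF can therefore score as a modest fall, a very large fall, a rise, or nothing.

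**How often this could arise.** Assume Hb change is normal with mean 1.0 g/dL, recorded to 0.1. At SD 0.5, about 0.7 of 40 patients have a falling Hb and 0.4 have exactly zero change. At SD 1.0 the counts are 5.9 and 1.0.

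**Simulation (n = 40, two-sided 5%).** OEF falls 5% on average, with SD 10% for the patient-level variation. The fall is either proportional to Hb (−5% per g/dL) or constant and unrelated to Hb. Patients with zero Hb change drop out of the ratio. Wilcoxon power, plain change versus per-patient ratio:

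| SD of Hb change | Proportional | Loss (points) | Constant | Loss (points) |
|---|---|---|---|---|
| 0.3 | 86 vs 80% | 6 | 85 vs 83% | 2 |
| 0.5 | 83 vs 71% | 12 | 85 vs 76% | 9 |
| 0.8 | 80 vs 67% | 13 | 85 vs 51% | 34 |
| 1.0 | 77 vs 69% | 8 | 86 vs 38% | 48 |

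Repeat runs agreed to within simulation error.

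**Size of the estimate.** Under the proportional effect the median ratio stays centred on −5.0, with the wrong sign in under 1% of trials at SD 0.5 and 1.0. Under the constant fall it averages −5.0, −4.7, −3.7 and −3.1 as the SD rises, with the wrong sign in 0.5%, 0.7%, 2.3% and 4.0% of trials. The ratio of group means (mean OEF change / mean Hb change) stays at about −5.0 under the constant fall, with a 95% range of −8.4 to −1.9 at SD 0.5 and −9.1 to −1.9 at SD 1.0.

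**Regression alternative.** The slope of OEF change on Hb change, with an intercept, averages −5.0 under the proportional effect. Its 95% range is −11.4 to +1.5 with 33% power at SD 0.5, and −8.2 to −1.8 with 84% power at SD 1.0. Under the constant fall it averages 0.0, because it measures association and not mean change.

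**The case against.** The best defence is that the paragraph's first sentence is already a complete primary analysis and agrees with sections 1, 2, 5.1 and 17.1, so the second sentence is naturally read as an additional way of expressing the result. A reader might infer that the scaled ratio replaces the primary endpoint, or that the plan leaves the primary quantity undefined. The documents do not support either: the endpoint table names plain change. That part of the defence stands, and it confines the fault to the one sentence. It does not remove the fault, because the sentence says the measures will be adjusted and does not call the result supplementary.

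Second, the plan never says that ratios are formed per patient. A ratio of group means or a regression adjustment also fits the words, and neither divides by an individual's near-zero Hb change. This stands too, and the numerical harm is conditional on the per-patient reading.

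Third, the largest losses need a fall in OEF unrelated to Hb, against the narrative hypothesis in section 3 ("We hypothesize that as hemoglobin increases due to voxelotor, cerebral blood flow and oxygen extraction fraction will decrease"), together with an Hb-change SD as large as its mean. That is fair. However, section 3 also reports that voxelotor raises Hb-oxygen affinity, so an effect on OEF not proportional to total Hb cannot be ruled out from the protocol itself. Nor is a loss of power universal. In a separate set of runs with residual SD 8%, a proportional effect, a mean Hb rise of 0.5 and SD 1.0, the Wilcoxon test on ratios had 59% power against 37% for the t-test on plain change.

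Fourth, section 17.2 calls the results descriptive and lists individual data by measure and time point, so plain changes remain recoverable. This limits the severity, although sections 17.1 and 17.2 do plan significance tests.

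Last, the plural subject of the sentence suggests that all three measures were meant. Even so, only the OEF form is given.

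**Conclusion.** The concern holds as a fault in one sentence of the primary analysis. That sentence requires a scaled quantity which is not the endpoint or the hypothesis, defines it for OEF only, and gives it no supporting label, although the Hb relationship already has a secondary endpoint.

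The division arithmetic is certain if ratios are formed per patient. The power losses of 6 to 13 points (proportional effect) and 2 to 48 points (unrelated effect) rest on that reading and on assumed values: mean Hb rise 1.0 g/dL with SD 0.3 to 1.0, and a 5% OEF fall with SD 10%. They illustrate the risk and do not predict this trial. The planned Wilcoxon option and the use of medians remove most of the instability of a mean of ratios, but not the sign reversal in individual patients.

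Severity is minor to moderate.

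**What to change.** In the primary-analysis paragraph of section 17.2, replace the adjustment sentence with: *The primary analysis is the unscaled within-patient change from baseline in CBF, OEF and CMRO2 at weeks 4 and 12, reported with 95% CI.* State whether change is absolute or percent of baseline.

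Report the Hb-related result as supportive or secondary, for all three measures, without individual patient ratios. Choose one of these in advance:

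- the ratio of group mean change to group mean Hb change, with a bootstrap 95% CI; or
- a regression of change in each measure on change in Hb, with an intercept, reporting the slope and 95% CI. Note that the slope answers the association question, is not mean change per g/dL, and may be imprecise if patients' Hb responses are similar.

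The cost is plan wording only, with no new data, visits or patients. The downside is that the Hb-normalised figure is no longer part of the primary result.
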